10.6.2 Primary and Secondary Tolerability Endpoints

The primary endpoints Change from Baseline of VAS Tolerability Scores in Study Eye at D2 Pre-Dose Visit and Changes from Multiple Dose Baseline of VAS Tolerability Scores in Study Eye at D2 8hr, D3 Pre-Dose, D6 Pre-Dose, D6 8hr, FU1 0hr, FU2 8hr, Fu3 0hr visits will be summarized for the SAF by treatment group.

For secondary analyses, the VAS tolerability Scores will be summarized for all scheduled assessment times by treatment separately for Study Eye and Non-Study Eye as well as the intra-individual differences between the eyes in subjects included in the SAF.

All collected and derived tolerability data will be listed for the SAF.

10.7 Additional Secondary Safety Assessments

10.7.1 ECG

For secondary analyses, the raw values as well as the changes from baseline of the endpoints ECG Heart Rate, PR interval, QRS duration, QT interval, QTcB interval, QTcF interval will be summarized by treatment for the SAF.

All collected and derived ECG data including investigator's interpretation will be listed for the SAF.

10.7.2 Vital Signs

For the secondary analyses, the raw values as well as the changes from baseline of the endpoints systolic and diastolic blood pressure (mmHg), pulse rate (bpm), respiratory rate (breaths/min) and oral body temperature (°C) will be summarized by treatment for the SAF.

All collected and derived vital signs data will be listed for the SAF.

10.7.3 Laboratory Safety Data

For the secondary analyses, the raw values as well as the changes from baseline haematology and chemistry (except of FSH) will be summarized by treatment for the SAF.

All collected and derived laboratory safety data will be listed for the SAF.

10.7.4 Intraocular pressure

Intraocular Pressure is summarized for the SAF by Study Eye/Non-Study Eye and treatment group at all visits as well as changes from baseline at all post-baseline visits.

A listing will present all documented assessments of intraocular pressure as well as the respective changes from baseline for the SAF.

10.7.5 Change in BCDVA

For the SAF, the Visual Acuity Score and logMAR will be summarized per Study Eye/Non-Study Eye respectively for each treatment group at all scheduled study visits as well as changes from baseline for all Post Baseline Visits.

All raw as well as derived BCDVA data will be listed for the SAF.

10.7.6 TFBUT

For the SAF, the Average TFBUT value will be summarized per Study Eye/Non-Study Eye respectively for each treatment group at all scheduled study visits as well as changes from baseline for all Post Baseline Visits.

All documented TFBUT values including all derivations will be listed for the SAF.

10.7.7 Ocular Surface Staining

For the SAF, corneal and conjunctival staining will be summarized per Study Eye/Non-Study Eye respectively for each treatment group at all scheduled study visits as well as changes from baseline for all Post Baseline Visits.

All documented staining results including all derivations will be listed for the SAF.

10.8 Other Safety Variables

External Ocular Examination (EOE)

All evaluations of the motility of extraocular muscle Right and Up, Right, Right and Down, Left and Up, Left, Left and Down will be summarized descriptively by treatment group and study visit for the Study Eye as well as the Non-Study Eye. This analysis will be performed on the SAF. These data will also be listed for the SAF.

Incidences of proven eyelid deformity/abnormality, abnormal motor function of eyelids, corneal exposure in case of closed eyelid, proven punctal occlusion, punctal plugs, thermal or surgical occlusion or other punctal occlusion will be presented for the SAF by treatment group and study visit for the Study Eye as well as for the Non-Study.

Moreover, these data will be listed for the SAF.

Slit Lamp Evaluation

All grading assessments of different eye structure (excluding assessment for other structures) will be summarized descriptively for the SAF by treatment group and study visit for the Study Eye as well as the Non-Study Eye.

All data recorded on the eCRF page 'Slit Lamp Examination (Biomicroscopy)' will be listed for the SAF.

Fundus Ophthalmology

All data including details on detected abnormalities recorded on the eCRF will be listed for the SAF clearly indicating the mode of assessment (Dilated/Not-Dilated).

Physical Examination

All physical examination data recorded on the eCRF will be listed for the SAF.

10.9 Pharmacokinetic Evaluations

All pharmacokinetic evaluations will be presented for the PKS.

Summary descriptive statistics for both absolute and time-matched changes from baseline will be provided by treatment for rhNGF serum concentrations ELISA I as well as ELISA II at all scheduled time points including geometric mean, coefficient of variation and 95% confidence intervals for the geometric mean.

In addition, presence of rhNGF concentrations will be summarized by treatment group for ELISA I and ELISA II concentrations at each scheduled assessment time.

Serum concentration versus time profiles will be presented on linear and log/linear scale for each individual with at least one value above detection level as well as geometric mean and median values for each time-point by treatment group. For individual plots, actual sampling times will be used. For the plots of geometric mean, scheduled sampling times will be used.

All recorded PK data will be listed for the SAF, clearly indicating subjects not included in the PKS.

Further PK analysis might be performed according to an appendix of the SAP, if indicated.

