2.6 A Summary Of Clinical Data

rhNGF has been already studied in healthy volunteers and in different subject populations.

In the completed Phase I study in healthy volunteers (study NGF0112), a total of 58 subjects (out of 74 enrolled) were treated with rhNGF. Furthermore, as of January 2016, in the Phase I/II and Phase II in subjects with NK (REPARO study NGF0212 and study NGF0214) a total of 174 and 48 subjects respectively have completed the two months treatment and in the Phase I/II in subjects with RP (LUMOS study NGF0113) 50 subjects have completed the six months treatment; furthermore, in the pilot Phase II study in subjects with dry eye (study NGF0213) 40 patients have completed the one month treatment with rhNGF.

The dose that is proposed for this study (20 µg /mL) has been already tested both in healthy volunteers for five consecutive days and subjects for up to six months. Besides higher doses of rhNGF (up to 180 µg /mL) were administrated for 168 days to retinitis pigmentosa subjects. Table 2 below summarizes the subjects exposed to date at different rhNGF eye drops concentrations:

In healthy volunteers no SAEs were recorded. Mild and transient ocular AEs possibly related to rhNGF administration were reported. rhNGF did not accumulate in serum after multiple doses and was detectable only in 6 subjects. Evaluation of vital signs, electrocardiograms, blood chemistry, urinalyses, and ocular

parameters indicated no evidence of rhNGF treatment effects. It can be concluded that at doses up to 180 µg/ml, rhNGF eye drops were well tolerated with no detectable clinical evidence of systemic AEs. Most of the ocular AEs were mild in severity and transient in nature.

In all studies rhNGF was well tolerated and the reported ocular AEs were generally transient and mostly mild and moderate in intensity during the controlled treatment period and the follow-up period.

Only moderate and transient ocular AEs possibly related to rhNGF administration were reported.

Table 2: Doses of rhNGF used in previous clinical studies in Europe and US

Doses of rhNGF in Human Healthy Volunteers						
Dose	per	Concentration	Frequency	of	Total	Dose
35 µL drop			Dose		per Day	Total Dose
Part 0, Ascending Single Dose: 1 drop, 1 treatment day						
0.0175 µg		0.5 µg/mL	once		0.0175 µg	0.0175 µg
0.175 µg		5 µg/mL	once		0.175 µg	0.175 µg
0.7 µg		20 µg/mL	once		0.7 µg	0.7 µg
Part A, Ascending Fractionated Single Dose: 1 drop, q4h (three times a day), 1 treatment day						

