The **Treatment Period** starts with the first intake of study medication and ends before the first assessment of the D7 visit. Any assessment before the first intake of study medication is allocated to the **Screening Period**. The **Follow-Up Period** of the study will start with the first assessment on the D7 visit.

Moreover, the Treatment Period is divided into **Treatment Period of the Single Dose Scheme**, which ends before the first intake of study medication on D2 and the **Treatment Period of the Multiple Dose Scheme**, which starts with the first intake of study medication on D2.

If not stated otherwise in subsequent sections, Baseline is defined as the first assessment of the D-1 Visit.

Change from Baseline is defined as the difference between an assessment and the respective first assessment at the Baseline Visit.

Change from Multiple Dose Baseline is defined as the difference between an assessment and the respective Pre-Dose assessment at the D2 Visit.

A **Time-Matched Change from Baseline** is defined as the difference between an assessment and the respective assessment at the corresponding time-point at the Baseline Visit.

Table 2: Study Visits

Scheduled Visit	Scheduled Visit Label	Scheduled Relative Assessment Times within Visit	Comments
Screening Visit	Screening	Before Baseline Visit	Acceptable time window for screening visit: Treatment Day -21 to Treatment Day -2
Baseline Visit	D-1	0 hr 0.5 hr 2 hr 4 hr 8 hr 9 hr 10 hr 11 hr 12 hr 14 hr 16 hr	Acceptable time window: Day before first dose
Treatment Day 1	D1	Pre-Dose 0 hr 0.5 hr 2 hr 4 hr 8 hr 9 hr 10 hr 11 hr 12 hr 14 hr 16 hr	Dosing should occur at 0 hr Time of dosing should be identical to respective time point at baseline visit.
Treatment Day 2	D2	Pre-Dose 0 hr 0.5 hr 2 hr 4 hr 6 hr 8 hr 10 hr 10.5 hr 11 hr 12 hr 13 hr 14 hr 16 hr	Dosing should occur at 0, 2, 4, 6, 8, 10 hr. Time of dosing should be identical to respective time points at baseline visit.

Scheduled Visit	Scheduled Visit Label	Scheduled Relative Assessment Times within Visit	Comments
Treatment Day 3	D3	Pre-Dose 0 hr 2 hr 4 hr 6 hr 8 hr 10 hr	Dosing should occur at 0, 2, 4, 6, 8, 10 hr. Time of dosing should be identical to respective time points at baseline visit.
Treatment Day 4	D4	Pre-Dose 0 hr 2 hr 4 hr 6 hr 8 hr 10 hr	Dosing should occur at 0, 2, 4, 6, 8, 10 hr. Time of dosing should be identical to respective time points at baseline visit.

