7.2.17 Pharmacokinetic Endpoints

Two validated ELISA tests performed at Dompé farmaceutici s.p.a. will be used for PK measurements. The original validated method (ELISA I) will be the same applied to the NGF determination in serum samples taken from studies NGF0112 and NGF0212. A new additional validated ELISA method (ELISA II) will be performed with the intention of improving the sensitivity in the determination of NGF serum levels.

Pharmacokinetics blood samples were taken on Baseline Visit 0 hr, 0.5 hr, 2 hr, 4 hr, 8 hr, 9 hr, 10 hr, 11 hr, 12 hr, 14 hr and 16 hr, for assessment of single dose scheme at D1 Pre-Dose, 0.5 hr, 2 hr, 4 hr, 8 hr, 9 hr, 10 hr, 11 hr, 12 hr, 14 hr and 16 hr, for multiple dose scheme at D2 Pre-Dose, 0.5 hr, 2 hr, 4 hr, 6hr, 8 hr, 9 hr, 10 hr, 10.5hr, 11 hr, 12 hr, 13hr, 14 hr and 16 hr, D3 Pre-Dose, 2 hr, 4 hr, 6 hr, 8 hr, 10 hr, D4 Pre-Dose, D5 Pre-Dose, D6 Pre-Dose, 4 hr, 8 hr, 10 hr, 10.5hr, 11 hr, 12 hr, 13 hr, 14 hr and 16 hr, FU1 0hr, FU2 0 hr and 8 hr, FU3 0hr.

The assessment times are documented on eCRF Pages “Pharmacokinetics – Anti-Therapeutic Antibodies”, the rhNGF serum concentration assessed via both ELISA methods will be provided as external Excel files by Dompé. To maintain masking, these files will be provided for BDRM purposes in a masked manner by utilizing a dummy subject identification. For the final analysis, the Excel Files will contain the correct subject identification number.

The concentration versus time profiles of NGF will be assessed from individual serum samples of all subjects. As a general principle, the nominal assessment times will be used.

For the rhNGF serum levels according to ELISA I and ELISA II time-matched changes from baseline will be presented for the PKS (excluding blood samples at 6 hr, 10.5hr and 13 hr).

For this purposes, values below the limit of detection will be set to a value of 1 pg/ml. However, for listings values below the limit of detection will be presented as “< 32 pg/ml” for ELISA I levels and ‘< 15 pg/ml’ for ELISA II.

A binary variable ‘Presence of rhNGF’ will be derived for each ELISA with ‘No’ indicating a value below the limit of detection and ‘Yes’ indicating a value above the limit of detection.

Beyond the respective rhNGF plasma levels for both ELISA methods, the following parameters will only be investigated for each ELISA method, if the data warrant to do so:

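### SAP 10.9 requests a geometric mean, its 95% CI and a CV for time-matched rhNGF changes, which are differences that can be zero or negative

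*SAP*

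**What the plan says.** SAP 10.9 states: "Summary descriptive statistics for both absolute and time-matched changes from baseline will be provided by treatment". The same sentence extends this to both assays "at all scheduled time points including geometric mean, coefficient of variation and 95% confidence intervals for the geometric mean". It sets no condition and draws no line between concentrations and changes. The change summaries are planned as Tables 14.6-1.2 (ELISA I) and 14.6-2.2 (ELISA II).

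SAP 7.1 says that a time-matched change is "defined as the difference between an assessment and the respective assessment at the corresponding time-point at the Baseline Visit". It is therefore a subtraction, not a ratio.

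SAP 7.2.17 introduces the time-matched changes, leaves out the 6, 10.5 and 13 hr samples, which have no Day -1 counterpart, and continues: "For this purposes, values below the limit of detection will be set to a value of 1 pg/ml". The limits shown for listings are 32 pg/ml (ELISA I) and 15 pg/ml (ELISA II).

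Four other places bear on the point:
- SAP 8.1 makes geometric statistics for pharmacokinetic parameters conditional on their being applicable, without a criterion.
- SAP 8.2 says, without condition, that 95% intervals for the geometric mean are calculated in the pharmacokinetic analysis.
- SAP 8.3.2 plans no imputation.
- SAP 7.2.17 allows a further PK appendix if one is required; SAP 13 lists none.

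**The concern.** A geometric mean, its log-based interval and a geometric CV need strictly positive data. Substituting 1 pg/ml makes the logarithm of a concentration computable, but a difference between two substituted values is zero and a difference from a detectable baseline may be negative. The plan therefore asks for a statistic that does not suit the variable and gives no rule for the cells where it fails.

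Tables are to be independently double programmed (SAP 5.3), so two programmers would each have to choose a handling that the SAP does not supply. If a program silently lost the non-positive changes when taking logs, the cell would show a geometric mean of the positive changes only. That would overstate systemic exposure in a table that serves the secondary, pharmacokinetic objective.

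**Working it through.** The documents give no numerical figure for this point, so there is none to reproduce. The check applies the SAP's own rules.

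**1. Values a change can take** (substitution from SAP 7.2.17, difference from SAP 7.1)
- Both samples undetectable: 1 − 1 = 0 pg/ml.
- Day -1 at the detection limit, later sample undetectable: 1 − 32 = −31 (ELISA I) or 1 − 15 = −14 (ELISA II).
- Both detectable, later value lower, for example 40 against 50: −10.
- Only the later sample detectable, at the limit: 32 − 1 = 31 or 15 − 1 = 14.

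**2. Effect on the statistics.** The geometric mean is exp(mean of ln d), its interval is built from the SD *s* of ln d, and the geometric CV is √(exp(s²) − 1). With zeros and no negative values, the geometric mean is 0 and the interval and geometric CV are undefined. With any negative value, the geometric mean has no meaning.

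**3. Number of cells** (sampling times in SAP 7.2.17, without 6, 10.5 and 13 hr)
- D1 11, D2 11, D3 5, D4 1, D5 1, D6 8, FU1 1, FU2 2, FU3 1. Total: 41 matched time points.
- Without the D2 9 hr sample, which SAP Table 2 does not list, the total is 40.
- Two groups × 41 = 82 cells per assay.
- Cells with no rhNGF exposure: 41 vehicle + 1 (rhNGF at D1 Pre-Dose) = 42.

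**4. Cells without exposure.** Assume that changes are as likely negative as positive, that subjects are independent, and that the groups are complete at 10 and 20. Ties at 0 only lower the chance of a positive change.
- P(all 10 vehicle changes positive) ≤ 0.5^10 = 0.00098, or 0.1%.
- Expected vehicle cells with all changes positive: at most 41 × 0.00098 = 0.04.
- rhNGF at D1 Pre-Dose: at most 0.5^20 = 0.0001%.

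**5. Dosed cells** (82 − 42 = 40 per assay). With q the assumed chance of a positive change per subject, P(all 20 positive) = q^20:

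| q | P(all 20 positive) |
|---|---|
| 0.90 | 12% |
| 0.95 | 36% |
| 0.99 | 82% |

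The documents do not give q. Protocol 2.6 says of healthy volunteers that "rhNGF did not accumulate in serum after multiple doses and was detectable only in 6 subjects", in a study where "a total of 58 subjects (out of 74 enrolled) were treated with rhNGF". ELISA I is the assay used there (SAP 7.2.17). This supports a q well below 1, but only qualitatively.

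**6. How far ad hoc handling could diverge** (invented data, for illustration only). Take n = 20, all Day -1 values and 18 later values undetectable, and two later values of 40 and 60 pg/ml. The changes are eighteen zeros, 39 and 59.
- Arithmetic mean: 98/20 = 4.9. Median: 0.
- Geometric mean of the positives only: √(39 × 59) = 48.0, from n = 2.
- Zeros replaced by 0.01, 0.1 or 1: geometric mean 0.023, 0.185 or 1.47.

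**The case against.** The best defence is that SAP 8.1 reports geometric statistics only where applicable. A statistic that cannot be computed is not applicable, so a sensible programmer leaves the cell blank. SAP 10 describes outputs by content and leaves layout to mock shells in a separate document, and a PK appendix can still be written before unmasking. This softens the point but does not remove it. SAP 8.1 gives no criterion and speaks of pharmacokinetic parameters, while SAP 8.2 and 10.9 are unconditional. What does stand is that the defect in the text is certain and a defective table is not: the shells may already omit these cells.

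A second defence is the SAP 7.2.17 rule that sets values below baseline to zero or missing. It belongs to the AUC definitions, and a zero still has no logarithm.

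On the CV, the Protocol synopsis and SAP 8.1 both pair it with the geometric mean, so a geometric CV is probably meant, although no formula is given. An arithmetic CV would exist wherever the mean change is not zero.

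The defence is right that the consequence is small. There is no inferential analysis, the arithmetic mean, SD, median and range remain valid, and detectability has its own tables (14.6-1.3 and 14.6-2.3).

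**Conclusion.** The point holds as a minor one. SAP 10.9 requests log-based statistics for a variable that the SAP's own rules make zero or negative. Failure is expected in nearly all 41 vehicle cells and at rhNGF D1 Pre-Dose, given the symmetry assumption, and is likely in many dosed cells unless almost every subject has a positive change.

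A reader might infer three stronger things that the documents do not support:
- **That exposure will be reported about ten times too high**, as in the illustration (48.0 against 4.9). That needs non-positive changes to be dropped. The SAP neither states this handling nor expressly excludes it, and the size depends on invented data.
- **That about 10% of changes will be positive**, from 6/58. The six are subjects in whom rhNGF was ever detected, not a share per time point. The documents do not say that all six were treated with rhNGF, and the regimens and ELISA II differ. A detectable value is also not the same as a positive change.
- **That the geometric summaries of absolute concentrations fail too.** With 1 pg/ml substituted, their logarithms exist. Whether SAP 7.2.17 means the substitution to cover those summaries is a separate question of wording.

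**What to change.** Before unmasking, add one sentence to SAP 10.9 and apply it to Tables 14.6-1.2 and 14.6-2.2: *The geometric mean, its 95% CI and the geometric CV are calculated for absolute concentrations only; time-matched changes are summarised by arithmetic mean, SD, median, minimum and maximum.* Masked PK data from both assays are required for the blind data review (SAP 8.3.3), so the matter can be settled there.

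The cost is one sentence, plus an edit to two table shells if they now show geometric statistics for changes. No new data or analysis is needed. The loss is the geometric statistics in the few change cells where every change happens to be positive. A geometric mean of ratios to the Day -1 value would be a computable alternative, but it adds a variable that the SAP does not define and would depend on the substituted 1 pg/ml.

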10.10 Immunogenicity

All recorded ATA concentrations will be listed for the SAF, clearly indicating subjects not included in the PKS.

11 References

1	Holladay, JT (1997) Proper Method for Calculating Average Visual Acuity. Journal of Refractive Surgery, 13, pp. 388-391
2	Lemp MA. Report of the National Eye Institute/Industry Workshop on clinical trials in dry eye. CLAO J1995, 21(4):221–32.

12 Tables, Listings and Figures

In agreement with Medical Writing, numbering of the actual output will be accommodated to numbering into appendices 14 and 16.

In the column U/R it is indicated whether the item is U=Unique TLF (or first instance of a table to be repeated) or R=Repeat item.

TLF number	Title	Analysis Set	U/R
Tables			
Table 14.1-1.1	Summary of Subject Disposition	TOT	U
Table 14.1-1.2	Summary of Study Discontinuation	SAF	U
Table 14.1-2.1	Summary of Protocol Deviations	SAF	U
Table 14.1-3.1	Summary of Demographics and Other Background Information	SAF	U
Table 14.1-4.1	Summary of Selected Study Eyes	SAF	U
Table 14.1-5.1	Summary of Medical History	SAF	U
Table 14.1-6.1	Summary of Prior Medications	SAF	R
Table 14.1-6.2	Summary of Concomitant Medications	SAF	U
Table 14.1-7.1	Summary of Exposure	SAF	U
Table 14.1-7.2	Summary of Compliance	SAF	U
Table 14.2-01.1	Summary of Primary and AE Related Secondary Endpoints	SAF	U
Table 14.2-02.1	Overall Summary of Adverse Events	SAF	U
Table 14.2-03.1	Summary of TEAEs by System Organ Class and Preferred Term	SAF	U
Table 14.2-04.1	Summary of TEAEs Single Dose by System Organ Class and Preferred Term	SAF	R
Table 14.2-05.1	Summary of TEAEs Multiple Dose by System Organ Class and Preferred Term	SAF	R
Table 14.2-06.1	Summary of FUAEs by System Organ Class and Preferred Term	SAF	R
Table 14.2-07.1	Summary of Ocular TEAEs by System Organ Class and Preferred Term	SAF	R

TLF number	Title	Analysis Set	U/R
Table 14.2-08.1	Summary of Ocular TEAEs in Study Eye by System Organ Class and Preferred Term	SAF	R
Table 14.2-09.1	Summary of Ocular TEAEs in Non-Study Eye by System Organ Class and Preferred Term	SAF	R
Table 14.2-10.1	Summary of TEAEs by Severity, System Organ Class and Preferred Term	SAF	U
Table 14.2-11.1	Summary of Treatment Related TEAEs by System Organ Class and Preferred Term	SAF	R
Table 14.2-12.1	Summary of TEAEs leading to Premature Withdrawal of Study Treatment by System Organ Class and Preferred Term	SAF	R
Table 14.2-13.1	Summary of TEAEs leading to Study Discontinuation by System Organ Class and Preferred Term	SAF	R
Table 14.3-1.1	Summary of VAS Ocular Tolerability Scores	SAF	U
Table 14.3-1.2	Summary of Changes from Single dose Baseline in VAS Ocular Tolerability Scores (Single Dose)	SAF	U
Table 14.3-1.3	Summary of Changes from Multiple Dose Baseline in VAS Ocular Tolerability Scores	SAF	U
Table 14.3-1.4	Summary of Intraindividual Differences between Eyes in VAS Ocular Tolerability Scores	SAF	U
Table 14.4-1.1	Summary of ECG Parameters	SAF	U
Table 14.4-1.2	Summary of Changes from Baseline in ECG Parameters	SAF	U
Table 14.4-2.1	Summary of Vital Signs	SAF	U
Table 14.4-2.2	Summary of Changes from Baseline in Vital Signs	SAF	U
Table 14.4-3.1	Summary of Haematology	SAF	U
Table 14.4-3.2	Summary of Changes from Baseline in Haematology	SAF	U
Table 14.4-4.1	Summary of Biochemistry	SAF	U

TLF number	Title	Analysis Set	U/R
Table 14.4-4.2	Summary of Changes from Baseline in Biochemistry	SAF	U
Table 14.4-5.1	Summary of Intraocular Pressure	SAF	U
Table 14.4-5.2	Summary of Changes from Baseline in Intraocular Pressure	SAF	U
Table 14.4-6.1	Summary of BCDVA Score	SAF	U
Table 14.4-6.2	Summary of Changes from Baseline in BCDVA Score	SAF	U
Table 14.4-7.1	Summary of LogMAR	SAF	U
Table 14.4-7.2	Summary of Changes from Baseline in LogMAR	SAF	U
Table 14.4-8.1	Summary of TFBUT	SAF	U
Table 14.4-8.2	Summary of Changes from Baseline in TFBUT	SAF	U
Table 14.4-9.1	Summary of Corneal and Conjunctival Staining	SAF	U
Table 14.4-9.2	Summary of Changes from Baseline in Corneal and Conjunctival Staining	SAF	U
Table 14.5-1.1	Summary of Motility of Extraocular Muscle	SAF	U
Table 14.5-2.1	Summary of Appearance and Function of Eyelid	SAF	U
Table 14.5-3.1	Summary of Slit Lamp Examination	SAF	U
Table 14.6-1.1	Summary of rhNGF titres ELISA I	PKS	U
Table 14.6-1.2	Summary of time-matched changes from Baseline in rhNGF titres ELISA I	PKS	U
Table 14.6-1.3	Summary of Presence of rhNGF Titres ELISA I	PKS	U
Table 14.6-2.1	Summary of rhNGF titres ELISA II	PKS	U
Table 14.6-2.2	Summary of time-matched changes from Baseline in rhNGF titres ELISA II	PKS	U
Table 14.6-2.3	Summary of Presence of rhNGF Titres ELISA II	PKS	U
Figures			
Figure 14.1-1.1	Plot of Geometric Mean and Median of rhNGF Titres by Time – ELISA I	PKS	U

TLF number	Title	Analysis Set	U/R
Figure 14.1-1.2	Individual rhNGF concentrations vs time plot – ELISA I (subjects with titres above detection level)	PKS	U
Figure 14.1-2.1	Plot of Geometric Mean and Median of rhNGF Titres by Time – ELISA II	PKS	NU
Figure 14.1-2.2	Individual rhNGF concentrations vs time plot – ELISA II (subject with titres above detection level)	PKS	NU
Listings			
Listing 16.1.7-1.1	Randomized Allocation of Study Treatment and Study Eye	TOT	U
Listing 16.2.01-1.1	Listing of Study Completion and Unmasking	TOT	U
Listing 16.2.02-1.1	Listing of Protocol Deviations	SAF	U
Listing 16.2.02-2.1	Listing of Deviations from Inclusion Criteria	SAF	U
Listing 16.2.02-2.2	Listing of Presence of Exclusion Criteria	SAF	U
Listing 16.2.03-1.1	Listing of Demographic Data	SAF	U
Listing 16.2.03-2.1	Listing of Smoking habits and alcohol consumption	SAF	U
Listing 16.2.03-3.1	Listing of Results of Alcohol Breath Test and Drug Screen	SAF	U
Listing 16.2.04-1.1	Listing of Medical History	SAF	U
Listing 16.2.04-2.1	Listing of Schirmer's Tear Test	SAF	U
Listing 16.2.04-3.1	Listing of Pregnancy Tests Results (Females only)	SAF	U
Listing 16.2.04-4.1	Listing of Results of Serology	SAF	U
Listing 16.2.05-1.1	Listing of Prior and Concomitant Medication	SAF	U
Listing 16.2.06-1.1	Listing of Study Drug Administration	SAF	U
Listing 16.2.07-1.1	Listing of Adverse Events	SAF	U
Listing 16.2.07-1.2	Listing of Action Taken due to Adverse Events	SAF	U
Listing 16.2.07-2.1	Listing of Ocular TEAEs	SAF	R
Listing 16.2.07-3.1	Listing of TEAES leading to Premature Withdrawal of Study Treatment	SAF	R

TLF number	Title	Analysis Set	U/R
Listing 16.2.07-4.1	Listing of TEAEs leading to Study Treatment Interruption	SAF	R
Listing 16.2.07-5.1	Listing of Treatment Related TEAEs	SAF	R
Listing 16.2.08-1.1	Listing of VAS Ocular Tolerability Scores	SAF	U
Listing 16.2.08-2.1	Listing of ECG Assessments	SAF	U
Listing 16.2.08-3.1	Listing of Vital Signs	SAF	U
Listing 16.2.08-4.1	Listing of Haematology Parameters	SAF	U
Listing 16.2.08-4.2	Listing of Biochemistry Parameters	SAF	U
Listing 16.2.08-4.3	Listing of Urinalysis Parameters	SAF	U
Listing 16.2.08-5.1	Listing of Intraocular Pressure	SAF	U
Listing 16.2.08-6.1	Listing of BCDVA Assessments	SAF	U
Listing 16.2.08-6.2	Listing of BCDVA Score, Snellen Equivalent and LogMAR	SAF	U
Listing 16.2.08-7.1	Listing of TFBUT Assessments	SAF	U
Listing 16.2.08-8.1	Listing of Ocular Surface Staining: Corneal Staining	SAF	U
Listing 16.2.08-8.2	Listing of Ocular Surface Staining: Conjunctival Staining	SAF	U
Listing 16.2.09-1.1	Listing of Motility of Extraocular Muscle	SAF	U
Listing 16.2.09-2.1	Listing of Appearance and Function of Eyelids	SAF	U
Listing 16.2.09-3.1	Listing of Slit Lamp Examination – Part I	SAF	U
Listing 16.2.09-3.2	Listing of Slit Lamp Examination – Part II	SAF	U
Listing 16.2.09-4.1	Listing of Fundus Ophthalmology	SAF	U
Listing 16.2.09-5.1	Listing of Physical Examination	SAF	U
Listing 16.2.10-1.1	Listing of rhNGF titres	PKS	U
Listing 16.2.10-2.1	Listing of ATA results	SAF	U

13 Appendices

None
